3.4 Outcomes

3.4.1 Primary Outcome

The primary outcome will be a symptom-based outcome. We will conduct a binary assessment of whether the participant is symptom free at Day 14 (yes or no) post enrollment.

3.4.2 Secondary Outcomes

Secondary outcomes will include

- **Hospitalization:** Defined as any visit to the emergency room or other hospital setting that resulted in a stay of 24 hours or more.
- **Adverse events:** we will conduct an adverse event survey at Day 3 after treatment, including gastrointestinal side effects (nausea, vomiting, diarrhea, abdominal pain) and rash. We note that some COVID-19 patients report gastrointestinal symptoms, and this survey will provide data on whether azithromycin causes additional gastrointestinal effects beyond those symptoms.
- **Prevalence of positive swabs:** we will compare the prevalence of SARS-CoV-2 positive swabs at Day 3 after treatment in self-collected nasal, saliva, and rectal swabs in azithromycin compared to placebo-treated participants.
- **Viral load:** we will assess viral load by RT-PCR in self-collected nasal, saliva, and rectal swabs at Day 3 after treatment.
- **Mortality:** we will collect emergency contact/next of kin information during the baseline questionnaire. We will follow-up with the emergency contact if participants are lost to follow-up at the Day 14 questionnaire to assess mortality and hospitalization outcomes.
- **Genetic macrolide resistance determinants:** We will evaluate the prevalence of genetic macrolide resistance determinants *ermB*, *mefA/E*, and *mphA* by targeted PCR in rectal samples collected at Day 3 after treatment.
- **COVID-19 symptoms:** we will ask patients about COVID-19 symptomology during each online questionnaire, including cough, fever, myalgia, anosmia, shortness of breath (and related abilities such as ability to walk across a room or up a flight of stairs), fatigue, conjunctivitis, and orthostatic symptoms.

- **Number of emergency room visits:** during each online questionnaire we will survey patients about any emergency room visits (with stays <24 hours) that occurred since their last survey.
- **Number of household members with COVID-19 (confirmed or symptomatic):** during each online questionnaire we will ask participants how many of their household members have symptoms of COVID-19 or confirmed disease.
- **Death:** we will attempt to link deaths among participants to the National Death Index.

3.5 Sample Size

The COVID-19 epidemic is changing rapidly over time. We propose a group sequential design with a flexible sample size that is adaptive to changing trial parameters over time with no maximum sample size. These designs are used in outbreak trials due to uncertainty with respect to parameters such as incidence and severity of outcomes. Full details on the sample size are provided in the Statistical Analysis Plan. In brief, the trial will employ a committee that is masked to results by arm that will evaluate the sample size on a weekly basis to evaluate the sample size based on the probability of hospitalization and enrollment.

On December 2, 2020 the DSMC members agreed to revise the sample size and primary outcome of the trial. Our re-estimated sample size of N=455 would allow for detection of a 15% absolute difference in probability of being symptom free at 14 days assuming that 50% in the placebo arm are symptom free (this is based on the current overall percent of participants who are symptom free at 14 days in ACTION). Because ACTION is enrolling more slowly than we had anticipated and we are planning a smaller sample size and we are also planning a single interim analysis at approximately 50% enrollment (N=230 participants), testing for efficacy at $p=0.001$, and then assess the final outcome at $p=0.049$.

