8.6 Laboratory Technicians

- Prepare patient study kits with all materials needed for the study
- Organize study supplies
- Prepare patient information sheets and swab instructions
- Scan swabs received from the participants into the REDCap database
- Assist with laboratory analysis of samples
- Assist with biobanking and storage of specimens

9 Statistical Methods

Please see the Statistical Analysis Plan for details on pre-specified statistical methods for this trial.

The primary analysis will estimate the risk difference (RD) and risk ratio (RR) comparing azithromycin to placebo. We will estimate these parameters using a logistic regression model with a single covariate for treatment arm. We will estimate the RD and RR from the logistic regression using marginal standardization, and a bootstrap for 95% confidence intervals [5,6]. We will compute *P*-values for differences between arms using a permutation test with the difference between arms as the test statistic and 10,000 iterations.

The secondary analysis of viral load will compare log transformed values of relative read and number of reads using a t-test. We will compute *P*-values for differences between arms using a permutation test with the difference between arms as the test statistic and 10,000 iterations.

Determination of statistical significance for the primary and secondary analysis will follow the final alpha-spending function determined by the group sequential design.

10 Study Medication

The study drug product will be obtained from Pfizer, Inc. Participants enrolled in the study will be offered a dose of oral azithromycin or placebo determined by their randomization allocation. We will monitor adverse events following treatment as described in Chapter 9.

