15.4 Procedures to Ensure Confidentiality and Proper Communication

To enhance the integrity and credibility of the trial, procedures will be implemented to ensure the DSMC has access to all emerging information from the trial regarding comparative results of efficacy and safety, aggregated by treatment arm.

Closed Sessions

Sessions involving only DSMC members and, where appropriate, those unmasked trial investigators (on the Data Coordinating Committee) who generate the Closed Reports (called Closed Sessions) will be held to allow discussion of confidential data from the trial, including information about the relative efficacy and safety of interventions.

At a final Closed Session, the DSMC will develop a consensus on its list of recommendations, including that relating to whether the trial should continue.

Open Session

In order for the DSMC to have access to information provided, by study investigators, or members of regulatory authorities, a joint session between these individuals and DSMC members will be held between the Closed Sessions.

Open and Closed Reports

For each DSMC meeting, Open and Closed Reports will be provided. Open Reports, will include data on recruitment and baseline characteristics, pooled data on eligibility violations, and completeness of follow-up and compliance. The study statistician ([name]) will prepare these Open Reports.

Closed reports, available only to those attending the Closed Sessions of the meeting, will include analyses of primary and secondary efficacy endpoints, including subgroup and adjusted analyses, AEs and symptom severity, and Open Report analyses that are displayed by intervention group. These Closed Reports will be prepared by the study biostatistician.

The Open and Closed Reports should provide information that is accurate, with follow-up that is complete to within two months of the date of the DSMC meeting. The Reports should be provided to DSMC members approximately three days prior to the date of the meeting.

Minutes of the DSMC Meeting

The research team will prepare minutes for the open portion of the meeting, including the DSMC's recommendations.

Recommendations to the Steering Committee (SC)

At each meeting of the DSMC during the trial, the committee will make a recommendation to the Steering Committee to continue or terminate. This recommendation will be based primarily on safety and efficacy considerations and will be guided by statistical monitoring guidelines defined in this Charter.

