15.5 Statistical Monitoring Guidelines

The SC will propose statistical rules for a futility stopping rule (requested by the sponsor) and an efficacy stopping rule at the first DSMC meeting.

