### 3.3. Sample size

The trial's revised target enrollment is 455 participants, which will be sufficient to detect an increase in the proportion of patients who are symptom free 50% to 65% (15 percentage point increase) at 14 days from enrollment.

With 455 participants, the trial will have 80% power to detect an increase of 15 percentage points in the percentage of patients who are symptom free at 14-d under the following assumptions:

- 2:1 allocation ratio of azithromycin : placebo
- 50% symptom-free under placebo at the 14-day measurement (binomial outcome)
- 20% loss to follow-up
- 2-sided alpha of 0.05, power = 0.8.

- A single interim analysis with 50% of primary outcomes collected with stopping guideline determined using the Lan-DeMets spending function approach with an O'Brien and Fleming boundary.

The table below shows sample sizes under several effect size scenarios, assuming azithromycin increases the proportion of patients who are symptom free by 0.1 to 0.2 compared to placebo.

Sample size required for a fixed design allowing for 20% loss to follow-up. Calculations assume 2-sided alpha of 0.05 and 80% power.

p placebo	p azithro	RD	N placebo	N azithro	N Total
0.5	0.60	0.10	348	695	1,043
0.5	0.61	0.11	287	573	860
0.5	0.62	0.12	240	479	719
0.5	0.63	0.13	204	407	611
0.5	0.64	0.14	175	349	524
0.5	0.65	0.15	152	303	455
0.5	0.66	0.16	133	265	398
0.5	0.67	0.17	117	233	350
0.5	0.68	0.18	104	207	311
0.5	0.69	0.19	93	185	278
0.5	0.70	0.20	83	165	248

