## One-sided group sequential design with
## 80 % power and 2.5 % Type I Error.
##

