## Analysis N Z Nominal p Spend
## 1 228 2.96 0.0015 0.0015
## 2 456 1.97 0.0245 0.0235
## Total 0.0250
##

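### Protocol 3.5 tests efficacy at the interim at p=0.001, but the SAP's spending function at 50% information gives two-sided 0.00305; one level, with its sidedness, is needed in both documents

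*Protocol*

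**What the plan says.** Protocol 3.5, in the paragraph on the revision agreed with the DSMC on December 2, 2020, plans a "single interim analysis at approximately 50% enrollment (N=230 participants"), "testing for efficacy at $p=0.001$, and then assess the final outcome at $p=0.049". It names neither a boundary method nor the sidedness. Protocol section 9 says that significance "will follow the final alpha-spending function determined by the group sequential design".

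SAP 3.3 specifies two-sided alpha 0.05, 80% power and "A single interim analysis with 50% of primary outcomes collected", with Lan-DeMets spending and an O'Brien-Fleming boundary. The design output in SAP 3.5 is headed "One-sided group sequential design with" 80% power and 2.5% type I error. Its interim row (analysis, N, Z, nominal p, spend) reads "1 228 2.96 0.0015 0.0015". The final row has N=456, Z=1.97 and nominal p=0.0245. The two-sided equivalents are not printed.

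The DSMC charter (Protocol 15.4) says that the recommendation to continue or terminate "will be guided by statistical monitoring guidelines defined in this Charter". Section 15.5 gives no level; it says only that the Steering Committee will propose a futility rule and "an efficacy stopping rule at the first DSMC meeting".

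**The concern.** The two documents describe the same single look at about half the trial but give different thresholds for it. Doubling the SAP's one-sided final p gives the protocol's 0.049, so the protocol pair appears to be on the two-sided scale. On that scale the SAP's interim level is about 0.003, three times the protocol's 0.001.

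The disagreement runs one way. A result between the two levels would support stopping for efficacy under the SAP and continuing under the protocol. The DSMC would then hold two thresholds, a charter with no number and no clause saying which document prevails. It would have to choose a rule after seeing the result, which pre-specification is meant to prevent.

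**Working it through.** **Inputs.** One-sided alpha 0.025, Lan-DeMets O'Brien-Fleming spending and information fraction t=0.5 (SAP 3.3 and 3.5). Protocol levels 0.001 and 0.049 (Protocol 3.5).

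**1. Reproduce the SAP boundary.** The spending function is a(t) = 2[1 − Φ(z(1−α/2)/√t)] with α=0.025.
- At t=0.5: 2.2414/√0.5 = 3.170, so a(0.5) = 0.001525. The interim bound is Z=2.963.
- The final bound solves P(Z1 < 2.963, Z2 ≥ c) = 0.025 − 0.001525, with correlation √0.5 between the two statistics. This gives c=1.969, one-sided p=0.0245.
- Both rows of the SAP table are reproduced. With drift 2.807 (80% power), the chance of crossing at the interim is 0.1641, as in the SAP output.

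**2. Put both documents on one scale.**

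| | Interim Z | Interim p, two-sided | Final Z | Final p, two-sided |
|---|---|---|---|---|
| SAP | 2.963 | 0.00305 | 1.969 | 0.0490 |
| Protocol, read as two-sided | 3.291 | 0.001 | 1.969 | 0.049 |

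**3. Try other readings of the protocol pair.**
- Both levels one-sided: overall one-sided alpha would be 0.0492, against the SAP's 0.025.
- Interim one-sided, final two-sided: interim Z=3.09, still not 2.96.
- Timing at 230/455 = 0.505: the SAP function gives two-sided 0.0032. It reaches two-sided 0.001 only at about t=0.41.
- Other boundaries: classic two-look O'Brien-Fleming gives 0.0052 two-sided, and the spending function applied to a total alpha of 0.05 gives 0.0056.

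None of these turns 0.001 into the SAP boundary. The pair does add to 0.05, so it may be a simple additive split; the documents do not say.

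**4. Consequence.** The mean of the interim Z under the design effect is 2.807 × √0.5 = 1.985.

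| Interim rule (final Z 1.969) | Crosses at interim, design effect | Overall power | Two-sided type I error |
|---|---|---|---|
| SAP, Z=2.963 | 16.4% | 80.0% | 0.0500 |
| 0.001 one-sided, Z=3.090 | 13.4% | 80.0% | 0.0496 |
| 0.001 two-sided, Z=3.291 | 9.6% | 79.9% | 0.0492 |

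With 0.001 two-sided, the interim result falls between the rules in 16.4% − 9.6% = 6.8% of trials under the design effect. Under the null the figure is 0.0015 − 0.0005 = 0.0010 in the upper tail.

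**5. Timing of the look.** The protocol counts enrollment; the SAP counts primary outcomes.
- The target of 455 includes an allowance for 20% loss, so planned evaluable outcomes are 455 × 0.8 = 364. Using the inflation that the SAP table follows (126 placebo × 1.2 = 151.2, rounded up to 152), they are 455/1.2 = 379.
- Half of these is 182 to 190 outcomes.
- If 230 enrolled participants are followed to Day 14 with 20% loss, about 184 outcomes result, and 184/364 = 50.5%. The two descriptions then nearly coincide.
- If the SAP's N=228 were read as 228 measured outcomes, the fraction would be 228/379 = 60% to 228/364 = 63%. The two-sided boundary would then be 0.0077 to 0.0092 at the interim and 0.0476 to 0.0471 at the end.

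**The case against.** The best answer is that the SAP governs. Protocol 3.5 refers to it for sample size details, section 9 refers to it for methods and ties significance to the spending function, and SAP 3.5 prints the boundary and promises to update it to the actual schedule. On this view 0.001 is a loose summary figure that could simply be deleted. The SAP is indeed the likelier authority, and deleting the figure with a reference to the SAP would also remove the conflict. But no clause says which document prevails. The protocol's sample size update is dated 12/18/20, after SAP version 6 of 2020-12-15, so the figure cannot be set aside as older text. The update clause does not explain it either, since both documents have one look at about 50%.

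A second objection is that the boundary is guidance: the DSMC advises, may weigh other outcomes, and the Steering Committee decides. That is so, and type I error and power hardly change. It limits the weight of the point, but guidance with two thresholds still has to be reconciled.

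Third, if 0.001 is one-sided and 0.049 two-sided, the gap shrinks to 16.4% − 13.4% = 3.0 percentage points, and the disputed zone to two-sided P between 0.002 and 0.00305. This stands as the lower end of the range. It requires mixed scales within one sentence, and the conflict remains.

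Finally, the timing difference has little effect if the 230 enrolled are followed to Day 14 before the look. It matters only if 228 is read as measured outcomes, so it is a side point.

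**Conclusion.** The inconsistency is real. The interim level of 0.001 in Protocol 3.5 does not follow from the spending function that both documents invoke, which gives two-sided 0.00305 at 50% information. The final level of 0.049 agrees once the sidedness is made explicit.

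Under the design effect, 6.8% of trials would have an interim result on which the documents disagree (3.0% on the mixed-sidedness reading), against about 0.1% under the null. Validity is not at risk: the protocol pair is slightly conservative, and overall power is practically unchanged. It should be fixed before the interim look.

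These figures assume one look at 50% information, normally distributed test statistics and the SAP's drift for 80% power. What the DSMC agreed on the interim level, beyond the protocol's account, cannot be seen from the documents.

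**What to change.** Before the interim look, state one interim level and its sidedness in both documents.

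- **If the SAP's spending function governs:** replace 0.001 in Protocol 3.5 with two-sided P ≤ 0.00305 (Z ≥ 2.963) and keep 0.049 for the final test. With 10,000 permutations P moves in steps of 0.0001, so the working threshold is 0.0030. The Monte Carlo standard error there is √(0.003 × 0.997/10,000) ≈ 0.0005, so more iterations at the interim would be sensible. Print the two-sided values beside the SAP's one-sided table.
- **If 0.001 two-sided is the level agreed with the DSMC:** change the SAP boundary to match. The final two-sided level could then be about 0.0498 for a total of 0.05.

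In either case, put the level in charter section 15.5 or refer there to SAP 3.5. Define the look in both documents by observed Day 14 outcomes, and name the planned number of evaluable outcomes (364 or 379) used as the denominator. If the spending function governs, recompute the boundary at the actual information fraction.

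The cost is a few sentences in Protocol 3.5, SAP 3.5 and the charter. No additional patients or data are needed.

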3.6 Masking

Investigators and participants will be masked to the treatment allocation. The following study procedures will be in place to ensure double-blind administration of study treatments.

- Access to the randomization code will be controlled
- A taste-matching placebo will be utilized
- Packaging and labeling of test and control treatments will be identical to maintain the blind.

The study blind will be broken upon completion of the clinical study and after the study database has been locked.

During the study, the blind may be broken only in emergencies when knowledge of the patient's treatment group is necessary for further patient management. When possible, the investigators should discuss the emergency with the Medical Monitor prior to unblinding.

3.6.1 Unmasking Protocol

If a patient and/or their doctor is concerned about a potential drug interaction or other medical issue, a discussion regarding a decision to unmask may come up.

If the patient has already taken the study medication:

1. [name] (PI) speaks with the patient and/or their treating doctor about the specific case. The decision will be made between the patient, the treating physician, and [name] about whether unmasking is necessary.
2. If no unmasking is required at the time, the issue is resolved. The patient and treating doctor can get back in touch if necessary.

3. If unmasking is required, we will take the following steps:

- a. We will only unmask a treating physician who is responsible for the patient's COVID care if deemed to be necessary for the care and safety of that patient. We will not directly unmask a patient. However, the treating physician may unmask the patient. The study team should advise the patient that it is very important that they do not inform us of what their study treatment was. As we are not involved in the patient's care, there is no reason for us to know their treatment assignment.
- b. The study team will inform [name] (ACTION biostatistician) of the patient's ID number and their treatment letters.
- c. [name] will call the patient's physician and relay this information to the physician. He will reiterate that the patient's physician should not disclose the treatment assignment to anyone on the study team except for him. [name] will have information available to him including the study dosing (1.2 g single dose as powder for oral suspension), when the patient was enrolled, and when the patient took the study drug (if known).
- d. [name] or his delegate will document the incident in an event log.
- e. Study staff will check in with the patient, encourage the participant to continue participating in the study, and remind them not to inform the study team of their treatment assignment.

If the patient has not yet taken the study medication:

1. [name] will speak with the patient and/or the patient's treating physician about the study. The decision will remain with the patient and their doctor as to whether the patient takes the study medication. No unmasking will occur, as any potential concerns can be avoided by simply not taking the study medication. We will ask the patient to document that they did not take the study medication on their follow-up form and the study team will document the event and the study team will encourage the patient to continue in the trial.

3.7 Study Period

Each participant will be in the study for a total of 21 days.

3.8 Main Study Timeline

| Timepoint | Activity |
|-----------|--|
| Day 0 | 
 • Eligibility Screening • Informed Consent • Baseline Questionnaire • Randomization |
| Day 1 | 
 • Treatment |
| Day 3 | 
 • Adverse events questionnaire • Self-collected nasal swab (opt-in) • Self-collected saliva swab (opt-in) • Self-collected rectal swab (opt-in) |
| Day 7 | 
 • Hospitalization and symptoms questionnaire |
| Day 14 | 
 • Hospitalization and symptoms questionnaire (primary endpoint) |
| Day 21 | 
 • Hospitalization and symptoms questionnaire |

4 Chapter 3: Study Eligibility

4.1 Inclusion Criteria

Participants must meet the following inclusion criteria to be eligible for this study:

- Evidence of a positive SARS-CoV-2 test and test results received within the previous seven days
- Not currently hospitalized
- Willing and able to receive study drug by mail
- Willing and able to return the internet-based study questionnaires at baseline, day 3, 7, 14, and 21 days via email or over the phone.
- No known allergy or other contraindication to macrolides
- No known history of prolongation of the QT interval (eg. History of torsades de pointes, congenital long QT syndrome, bradyarrhythmia).
- No recent use of hydroxychloroquine within the past 7 days for participants >55 years of age.
- Not currently taking nelfinavir or warfarin (Coumadin)
- Age 18 years or older at the time of enrollment
- Not currently pregnant
- Provision of informed consent

4.2 Exclusion Criteria

Participants will be excluded if they meet any of the following criteria:

- Negative or no SARS-CoV-2 test and test results not received within the previous seven days
- Currently hospitalized
- Not willing and able to receive study drug by mail
- Not willing and able to return the internet-based study questionnaires at baseline, 3, 7, 14 and 21 days via email or over the phone
- Known allergy or contraindication to macrolides
- History of known prolongation of the QT interval (e.g., history of torsades de pointes, congenital long QT syndrome, bradyarrhythmia)
- Recent use of hydroxychloroquine (past 7 days) for participants >55 years of age
- Currently taking nelfinavir or warfarin
- Younger than 18 years old at the time of enrollment
- Currently pregnant
- No provision of informed consent

5 Chapter 4: Study Methods

